During phase 2 (intervention), the self-administered RLPT will be implemented in the Child and Youth Center (CYC, the general pediatric clinic) and the Primary Care Adolescent and Child Clinic (PCAC) at UIH with all PP women bringing infants for the 2-month WBV. The intervention leverages an existing system designed to screen all PP women (through 6-months) for depression. Currently, when a mother checks-in her infant for a visit she is provided an Edinburgh Postpartum Depression Screening tool with instructions to complete and return the tool to the infant's physician during the visit. On a daily basis, completed tools are scanned and saved on a secure server (required for billing purposes). This system has been successful for universal PP depression screening and referral. An audit found that in 91% of all WBVs with a child 0-16 wks., the infant's mother was present and eligible to have an Edinburgh tool completed; of these, 90% had a completed Edinburgh tool provided to the physician. We will pair the RLPT with the Edinburgh tool (back to back on the same piece of paper); women of 2-month olds will be instructed to complete both sides. To test the feasibility of this approach, we briefly tested locating a general women's health screening survey on the back of the Edinburgh tool. During the pilot, 37 infants 0-16 wks. of age had a WBV; 89% of these had a complete Edinburgh. Of those who completed the Edinburgh, 100%

completed the survey on the opposite side, suggesting women are willing to complete another brief questionnaire.

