Participant Eligibility: Postpartum women 15-49 years presenting with their infants to the CYC or PCAC for a 2-month WBV, and who also receive their own care at UIC (needed for chart abstraction purposes), are eligible to participate in the study. Women must be English and Spanish speakers.

Participant Exclusion: Women who are currently pregnant, less than 15 years or older than 49 years of age, or do not speak English or Spanish.

Participant Recruitment into the Research Study: The intervention is planned as a system-level intervention, thus, all women whose infants are scheduled for a 2-month WBV during the intervention period will have the opportunity to be exposed to the RLPT intervention. On study recruitment days (randomly selected half-days during phase 2), women whose infants are scheduled for a 2-month WBV will be approached by a

research assistant (RA) who will screen for eligibility. Recruitment into the study will occur before, during or after the WBV, baseline surveys will be completed during or after the WBV to avoid biasing women's responses on the RLPT, which is administered *prior* to the WBV. If a woman is eligible and interested in participating, she will be consented and asked if she has time to complete a baseline survey. The baseline survey will include the domains listed in Table 1. To the extent possible, the baseline survey will be self-administered using a tablet computer linked to the RedCap database. A study RA will be available to provide assistance or administer the survey if necessary. When possible, the surveys will be completed immediately after the WBV in a private room. We are sensitive to the fact that women may not have the time to stay after the WBV, in which case we will request permission to conduct the survey by phone at a convenient time. Our research team has extensive experience recruiting PP participants and we have found this to be an effective strategy. Because this is a system-level intervention, women who decline participation in the study will still receive the intervention but will not participate in any research data collection. For example, a woman who does not agree to participate in the study would still have been given the RLPT prior to the infant's visit and, if desired, she will receive a referral and appointment for care though she will not be included in the study.

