with pediatricians weekly during the first 4 weeks of the study, and monthly thereafter, to answer questions and encourage consistent provider use of the tool. We will schedule a ‘refresher’ training 3 months after the start of the study to reinforce appropriate use of the tool. During the training, physicians will be instructed on how to start a conversation with women, what to document on the tool, and how to initiate a referral if needed. Physicians are *not* expected to provide contraceptive counseling to mothers, only to engage women in a discussion about their health care needs. An information sheet about the study will be given to all pediatric providers who are trained.

Selection of control group: The control group will be enrolled during phase 1 (first 4 months) prior to the introduction of the intervention. Similar to the intervention group, women will be recruited by an RA before, during or after the health care visit and screened for eligibility. Informed consent will be obtained for a baseline survey using the same procedure as described for the intervention group (same gift card amounts). Because we are studying health behaviors, we cannot share the specific aims of the study with control group participants as this could bias behavior. The control group participants will be told that this is a study monitoring women’s general health care experiences at UIH. After enrollment of the control group, a 6-week washout period prior to phase 2 (intervention) will ensure women are not enrolled into both arms of the study.

Sample: This pilot study will enroll at least 50 women per group. This sample size will provide a stable estimate of the intervention’s effect on primary care receipt by 6 months postpartum for power calculations for a larger, subsequent study of intervention effectiveness. There are approximately 200 deliveries per month at UIH, with 57% (114) of these infants having a 2-month WBV at UIH. For the 4-month period of recruitment each for control and intervention groups, we can meet our target enrollment of 50 in each group by recruiting women during four of the ten half-day CYC clinics per week, assuming a conservative participation rate of 40%.

Table 1 Study Variable Table

Variable	Specific Aim	Level of Measurement	Time of Collection	Tool	Variable Type
Demographic Data	I	Women	Enrollment	Baseline survey	Covariate
Physician Characteristics Male/Female, Trainee/Faculty	II	Physicians	Enrollment	Medical record schedule	Covariate

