Clinical Operations Visit time and day of week	II	Health System	Enrollment	Medical record schedule	Covariate
Health and Family Planning					
Women’s general health status	I	Women	Enrollment	Baseline Survey	Covariate

Women's general health behaviors (smoking, alcohol, nutrition and exercise)	I	Women	Enrollment	Baseline Survey	Covariate
Plans for future pregnancy	I	Women	Enrollment	RLPT	Covariate
Current contraception type and use	I	Women	Enrollment	RLPT	Covariate
Pregnancy status	I	Women	6 months postpartum	Phone survey and Chart review	Dependent
Referral to primary care	I	Women	Enrollment	RLPT	Dependent
Receipt of primary care visit	I	Women	6 months postpartum	Phone survey and Chart review	Dependent
Use contraception, duration and method	I	Women	6 months postpartum	Phone survey and Chart review	Dependent
Feasibility, Acceptability, and Adoption of RLPT					
Ease of use, comfort and satisfaction with tool	II	Physician	Year 2	Focus groups	Acceptability
Ease of use, comfort and satisfaction with tool	II	Women	Enrollment	Baseline survey	Acceptability
Women's need and desire for referral	I and II	Women	Enrollment	RLPT	Acceptability
Women's barriers and facilitators	II	Women	6 months postpartum	Phone survey and Chart review	Feasibility
Physician barriers and facilitators	II	Physician	Completion of study	Focus groups	Feasibility
Completion rate for grey box on RLPT form	II	Health System	Enrollment	RLPT completion rate by women and physicians	Adoption

Data Sources and Collection

Surveys of Women: All participants will complete a baseline survey (English and Spanish) at the time of enrollment in the study (during or after the WBV) and will receive

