a phone call at 6 months PP for the follow-up survey (survey and interview questions domains listed in Table 1). During the baseline survey, in addition to demographic information, women will be asked about their general health status and health behaviors, and current contraception type and use. Those in intervention arm will be asked about their experience completing the RLPT during the WBV, referral to well-woman primary care (if applicable). For the follow-up survey we will try to reach each participant as close to 6 months as possible, but no later than 9 months PP. Structured phone interviews with women will include questions from the following domains: 1) use of health care services; 2) use and type(s) of contraception; and 3) known pregnancy status. The intervention group interviews will also include experience completing the RLPT during the WBV; and, the process of getting care (for those who chose to do so) (SA II). To verify RLPT exposure at the individual level, the RLPT tool will be linked to the mother using the patient sticker placed on the tool.

Medical Records: Medical records will be reviewed at baseline and at 6 months PP to determine receipt of health care services and contraception. We recognize that some women may receive additional health care outside the UIC system; for this group, we will not be able to confirm medical visits outside the UIC system.

Focus Groups with Providers: We will conduct two in-depth qualitative focus groups with physicians (residents and faculty) after the intervention is complete during study year 2. The focus group guide will include questions from the following domains: 1) Experience implementing the RLPT; and, 2) barriers and facilitators to implementation of RLPT (SA II). In addition, study investigators will keep a running log of barriers and facilitators experienced throughout the intervention implementation period.

Data Management

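### Pregnancy plans (Aim I covariate) and referral (Aim I dependent variable) have no stated source in the control group, so the first cannot be balanced or adjusted for and the second cannot be compared

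*Combined protocol and SAP*

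**What the plan says.** All references are to the combined protocol and SAP.

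- **Table 1 Study Variable Table.** "Plans for future pregnancy" is an Aim I covariate and "Referral to primary care" an Aim I dependent variable. Both are collected at enrollment, and the RLPT is the only tool named. Current contraception is also an Aim I covariate with the RLPT as its only listed tool.
- **Study Design and Intervention.** "During phase 2 (intervention), the self-administered RLPT will be implemented in the Child and Youth Center" and in the second pediatric clinic.
- **Selection of control group.** "The control group will be enrolled during phase 1 (first 4 months) prior to the introduction of the intervention".
- **Data Sources and Collection, Surveys of Women.** Besides demographics, at baseline "women will be asked about their general health status and health behaviors, and current contraception type and use". A further baseline block is limited to one group: "Those in intervention arm will be asked about their experience completing the RLPT during the WBV, referral to well-woman primary care (if applicable".
- **Data Sources and Collection, Medical Records.** "Medical records will be reviewed at baseline and at 6 months PP to determine receipt of health care services and contraception".
- **Analysis, Specific Aim I and Ia.** Baseline characteristics are tested across groups, and those found unbalanced enter a logistic model. The model has two outcomes: a primary care visit by 6 months and contraceptive use at 6 months.

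**The concern.** The comparison is between two cohorts enrolled one after the other, without randomisation. Its protection against confounding is the baseline balance check, followed by adjustment. A covariate can serve that purpose only if it is measured in both groups. Pregnancy intention is a plausible confounder of contraceptive use, because a woman who wants another child soon has less reason to use a method. It is therefore one of the more useful covariates for Aim Ia, and it is the one assigned to a form that controls never see.

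Referral is the step between the tool and the visit. Table 1 labels it dependent under Aim I, which implies a comparison of groups, but the plan names no way to learn how often controls were referred under usual care. A usual-care rate of zero cannot be presumed: the Background says that pediatric providers are open to referring mothers, and the clinics already screen and refer for depression. For a pilot meant to inform a larger study, knowing whether referral rose would help in reading either a positive or a null result on visits.

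**Working it through.** **The plan's own figures.** The recruitment arithmetic in the Sample paragraph reproduces and is not in dispute: 200 × 0.57 = 114 visits a month, and 114 × 4 months × 4/10 sessions × 0.40 = 73, above the target of 50 per group.

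**Step 1. Trace each variable to its source by group.**

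| Variable | Tool in Table 1 | Baseline survey, all women | Baseline survey, intervention only | 6-month call, all women | Chart review | Control value? |
|---|---|---|---|---|---|---|
| Pregnancy plans | RLPT | not listed | not listed | not listed | not listed | none |
| Referral | RLPT | not listed | yes | not listed | not named | none |
| Current contraception (baseline) | RLPT | yes | – | – | yes | yes |
| Primary care visit by 6 months | phone survey and chart | – | – | yes | yes | yes |
| Contraception at 6 months | phone survey and chart | – | – | yes | yes | yes |

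The domains of the 6-month call for all women are service use, contraception and known pregnancy status. Questions on the process of getting care are added for the intervention group only.

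**Step 2. Consequence for the balance check.** With pregnancy plans recorded only on the RLPT, the cross-table of plans by group has an empty control column, so the planned chi-square test cannot be computed.

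**Step 3. Consequence for the model.** Suppose pregnancy plans were nevertheless entered as x₂:

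logit(y) = β₀ + β₁x₁ + β₂x₂

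With 50 women per group, the complete cases are 0 controls and 50 intervention women. Every remaining row has x₁ = 1, so that column equals the intercept column. The design matrix has 3 columns and rank 2. Only the sum β₀ + β₁ can be estimated; β₁, and with it the adjusted relative risk and risk difference, cannot.

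**Step 4. What an unadjusted imbalance could do (illustration only).** The documents give neither the difference in pregnancy plans between groups nor its association with contraceptive use. As a rough guide, bias in the Aim Ia risk difference ≈ (difference in prevalence) × (association with the outcome):

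- assumed 10-point difference and 20-point association: 0.10 × 0.20 = 0.02, or 2 points;
- assumed 20-point difference and 40-point association: 0.20 × 0.40 = 0.08, or 8 points.

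For scale, the 95% half-width of a crude risk difference with 50 per group is 1.96 × √(2p(1 − p)/50). This is 0.180 at p = 0.3 and 0.196 at p = 0.5 (both p assumed). On these assumptions the bias is smaller than the sampling error, but unlike sampling error it does not shrink in a larger study of the same design.

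**Step 5. Referral.** The Analysis section gives no model, test or coding rule for referral. There is no planned estimate whose bias could be calculated.

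**The case against.** The strongest reply is that Table 1's tool column is not exhaustive. Current contraception is listed there under the RLPT alone, yet the baseline survey asks all women about it. The recruitment section also says "The baseline survey will include the domains listed in Table 1", and controls follow the same baseline procedure. On that reading pregnancy plans may already be on the common survey, and the instrument itself is not among the documents. This leaves some doubt about what the survey contains. It does not settle the matter: Table 1 assigns other rows explicitly to the baseline survey and this one to the RLPT, and the itemised survey content omits it. At best the sections disagree and need reconciling.

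Second, the plan adjusts only for characteristics found unbalanced, so a variable with no control data would never be flagged and the rank-deficient model would not be fitted. That is right. The practical loss is one confounder left unexamined, not a failed analysis.

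Third, both modelled outcomes come from sources used in both groups, so the main estimates do not depend on either variable. That also stands.

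Three stronger conclusions might be inferred, and the documents support none of them:

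- *That the effect on referral will be overstated by the usual-care referral rate, because controls are counted as zero.* No between-group analysis of referral and no zero coding are planned.
- *That a control referral rate would separate the effect of the tool from that of scheduling help.* The intervention bundles the two, and scheduling help exists only in phase 2.
- *That baseline contraception is also missing in controls.* It is surveyed in both groups; only the Table 1 label is incomplete.

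**Conclusion.** The point holds within limits. Followed as written, the plan yields no control value for pregnancy plans or for referral. Pregnancy intention cannot be balance-tested or adjusted for, which matters mainly for Aim Ia, and referral can be described only in the intervention group despite its label as an Aim I dependent variable.

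The crude relative risks and risk differences for visits and contraception can be computed as planned. No size of bias should be claimed for referral. The 2 to 8 points for Aim Ia are an illustration on assumed inputs, not a finding.

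The conclusion assumes that the itemised survey, interview and chart contents are complete. If the survey instrument already asks all women about pregnancy plans, that half of the point reduces to a correction of Table 1; the referral half remains. The change is worth making before enrolment, because pregnancy plans at enrolment cannot be reliably recovered later.

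**What to change.** Before phase 1:

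1. **Pregnancy plans.** Add one pregnancy-intention item to the baseline survey used in both groups and name that survey as the Table 1 source. Use the survey answer, not the RLPT answer, for the balance check and any adjustment. Intervention women answer it after completing the RLPT, so their RLPT answer can serve as a check on whether the visit shifted the response.
2. **Current contraception.** Name the baseline survey as its Table 1 source. No new data are needed.
3. **Referral.** Choose one of two options:
   - Ask both groups the same question at the 6-month call. Add chart abstraction of referral orders if the consent covers it, and state which record holds the order, since the request is made at the infant's check-out. The described consent to records access concerns services received, so coverage of referral orders must be confirmed.
   - Relabel referral as an intervention-group process measure under Aim II and drop the Aim I dependent label.

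The cost is one or two survey items and, if chosen, a chart field with a possible consent change. A referral question at the 6-month call relies on recall over about four months (6 − 2) or more, as calls may run to 9 months. The pregnancy-intention item may slightly prompt controls, from whom the aims are deliberately withheld, although they are already asked about contraception at baseline.

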assess women's need for well-woman primary care, then refer and provide an appointment for care for women who desire one.

Specific Aims

Aim I. To determine if introducing a self-administered Reproductive Life Planning Tool (RLPT) with postpartum mothers during the 2-month WBV will increase the proportion of women receiving a well-woman primary care health visit by 6 months postpartum.

Aim Ia. To determine if introducing a self-administered Reproductive Life Planning Tool (RLPT) with postpartum mothers during the 2-month WBV will increase utilization rates of contraception by 6 months postpartum.

Aim II: To assess the extent of system adoption as well as patient-, provider-, and systems-level barriers and facilitators to integrating a self-administered Reproductive Life Planning Tool designed to facilitate referral of postpartum women for primary well-woman care within the context of a pediatric clinic.

Study Design and Intervention

This is a single-site system-level pilot study to measure the impact of a self-administered RLPT (attachment) during the 2-month WBV on PP women's subsequent receipt of primary health care and contraception, compared to usual care. To facilitate women's uptake of a referral for well-woman primary care, women will be offered the opportunity to schedule a visit for herself on the same day as her infant's next WBV or the first available visit if she needs more immediate care. This study will have two phases: **phase 1** is enrollment of a control or baseline group, followed by a washout period; **phase 2** is enrollment of the intervention group (intervention).

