All survey data will be directly entered into REDcap web-based data capture screens that will be programmed and tested prior to the study. Data will be imported to SAS for analysis. Variables (Table 1) will be merged across time point by study ID and cleaned and recoded. Focus groups will be recorded, transcribed, and uploaded to DeDoose qualitative analysis software. Completion of the Grey Box (physician section of the tool) will be a measure of provider “adoption” of the intervention; completion rates will be tracked by comparing completed forms with completed clinic visits for 2-month WBVs. Completed clinic visit data are available in our existing medical record scheduling system.

Analysis

Specific Aim I and Ia: Baseline characteristics will be assessed for equivalency across groups using chi-square tests for categorical and t-tests for continuous variables. Unbalanced characteristics will be adjusted for in further analyses. The primary outcome, receipt of primary care services for women by 6 months PP (SA I) will be ascertained both by self-report during the 6-month phone interview and by medical record review, in order to minimize missing data. Evidence of a visit from either source

will be counted as receipt. Utilization, type and duration of contraception (SA 1a) by 6 months PP will be assessed similarly. An intent-to-treat analysis will be performed for SA I and 1a. A crude relative risk (RR) and risk difference (RD) will be calculated with 95% confidence intervals to estimate the effect of the intervention on primary outcomes. If adjustment is needed for covariates, RRs and RDs will be estimated using the average marginal predictions from a fitted logistic regression model with the following form:⁴¹

$$\text{logit}(y) = \beta_0 + \beta_1x_1 + \beta_2x_2 + \dots + \beta_kx_k, \text{ where:}$$

y =	SA 1: Woman's primary care visit by 6 months (1 = Yes/0 = No)
	SA 1a: Use of contraception at 6 months (1 = Yes/0 = No)
x ₁ =	RLPT Intervention (1 = Intervention/0 = Control)
x ₂ – x _k =	Unbalanced covariates

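### Prior use of care can be read from the planned baseline chart review but is not named as an Aim I covariate, so adjustment for it in this non-randomised phase comparison is left to chance

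*Combined protocol and SAP*

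**What the plan says.** Study Design and Intervention describes two consecutive phases: phase 1 "is enrollment of a control or baseline group, followed by a washout period", and phase 2 enrols the intervention group. There is no randomisation.

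Under Data Sources and Collection, Medical Records: "Medical records will be reviewed at baseline and at 6 months PP to determine receipt of health care services and contraception". Participant Eligibility requires that women receive their own care at UIC, so a chart should exist for every participant. The same paragraph concedes a limit on the chart: "we will not be able to confirm medical visits outside the UIC system".

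In Table 1, "Receipt of primary care visit" appears once, for Aim I, at 6 months postpartum, as a dependent variable. The Aim I covariates are demographics, general health status, health behaviours, plans for future pregnancy, and the row "Current contraception type and use". The Aim Ia outcome, contraception, therefore has an enrollment covariate row, and the primary outcome has none. The description of the baseline survey does not mention earlier care either: beyond demographics, "women will be asked about their general health status and health behaviors, and current contraception type and use".

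Data Management says that the Table 1 variables are the ones merged for analysis. In the Analysis section for Aims I and Ia, baseline characteristics are compared by chi-square and t-tests, and then "Unbalanced characteristics will be adjusted for in further analyses". No significance level or imbalance threshold is given.

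**The concern.** Women who have already been using care for themselves may be more likely to have a visit by 6 months. If the women enrolled in phase 2 are more or less engaged with care than those enrolled in phase 1, that difference enters the RR and RD as if it were an intervention effect. Randomisation would make such a difference a matter of chance. Here, calendar time and selection into the study (40% participation is assumed) can produce it systematically.

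Prior care is close in kind to the outcome, is fixed before the tool is handed out, and can be abstracted in the same way in both phases. The Sample section says that the pilot's effect estimate will inform power calculations for a larger study. Required sample size varies with the inverse square of the RD, so an error of a few points carries forward.

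**Working it through.** **1. The plan's own figures.** From the Sample section: 200 deliveries × 57% = 114 two-month visits a month, which reproduces. Over 4 months, at 4 of 10 half-days and 40% participation: 114 × 4 × 0.4 × 0.4 = 73 per group, which covers the target of at least 50. No power or effect size is stated, so the 50 cannot be checked against one. I use n = 50.

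**2. Assumptions that are not in the plan.**
- Prevalence of prior care is 53.7% on average over the two groups. The Background gives this figure as an upper bound on postpartum-visit attendance among Illinois Medicaid women. It is only a proxy here.
- The 6-month visit rate is 30% without prior care, and 20 or 40 points higher with it.
- The true imbalance in prior care between phases is 10 to 20 points.
- The balance test is two-sided at 5%, and the true intervention effect is zero.

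**3. Precision of the RD.** Half-width of the 95% CI = 1.96 × √(2p(1−p)/50). At p = 0.30 this is 0.180, at 0.50 it is 0.196, and at 0.60 it is 0.192: about 18 to 20 points.

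**4. Would the balance test catch an imbalance?** Power = Φ[(d − 1.96·SE₀)/SE₁], where SE₀ = √(2 × 0.537 × 0.463/50) = 0.0997 and SE₁ is the unpooled standard error.
- d = 0.10: SE₁ = 0.0992, power 17%.
- d = 0.15: SE₁ = 0.0986, (0.15 − 0.1955)/0.0986 = −0.46, power 32%.
- d = 0.20: SE₁ = 0.0977, power 52%.

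If one group has 27/50 with prior care, the other must reach 37/50, a 20-point difference, before the test is significant. With the expected yield of 73 per group, SE₀ = 0.0825 and SE₁ = 0.0816, and power at 15 points is still only Φ(−0.14) = 44%.

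**5. Size of the bias.** Without adjustment, bias in the RD ≈ imbalance × gap in visit rates. I compared this with a simulation of 15,000 runs per scenario. The adjusted estimate was standardised over prior care, which equals the marginal prediction from a logistic model saturated in group and prior care. Mean false RD, in percentage points:

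| Imbalance | Gap | Product | No adjustment | Adjust only if p < 0.05 | Always adjust |
|---|---|---|---|---|---|
| 10 | 20 | 2 | +2.1 | +1.2 | +0.1 |
| 10 | 40 | 4 | +4.0 | +2.1 | −0.1 |
| 20 | 20 | 4 | +4.2 | +1.2 | +0.2 |
| 20 | 40 | 8 | +8.1 | +2.2 | +0.1 |

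The SD of the RD was 0.098 to 0.100 without adjustment and 0.093 to 0.099 with adjustment in every run. Always adjusting therefore costs essentially no precision, and gains little when the gap is 20 points.

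**6. Can the covariate overlap the outcome?** The outcome is a visit by 6 months postpartum, with no start date. A woman's own postpartum primary care visit before the index WBV would already satisfy it. If the covariate were any primary care visit before the index WBV, every woman with such a postpartum visit would have the outcome by definition. The model would then condition on part of the outcome, and if most prior visits were postpartum it would approach separation. The two windows must be kept apart.

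**The case against.** A reader might infer that the plan rules out adjustment for prior care. It does not. The Analysis section speaks of baseline characteristics generally, and Table 1 is visibly not exhaustive: it sources current contraception from the RLPT alone, although the baseline survey and the chart review also collect it. Prior care could be tested and, if unbalanced, adjusted for. That stands. What the plan lacks is any commitment to do so, and the step 4 power shows how little a discretionary test would protect.

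The link between prior care and the outcome is assumed. The documents give no visit rates by prior care. The Background calls the approach particularly relevant to women who miss the postpartum visit, and those women might respond more to referral. Neither the sign nor the size of a bias is established, and calling prior care the strongest predictor would be judgement. That also stands.

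Two stronger readings should be resisted.
- By chance alone, an imbalance above 10 points has a probability of about 32% at this size (SD 0.0997). The resulting shift in the RD is sampling variation that the CI already reflects. Only a systematic phase difference is bias, and the documents give no figure for one.
- A difference between phases in postpartum-visit attendance might be read as showing drift, and its absence as excluding drift. At 50 per group it can do neither.

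Finally, a chart limited to UIC care misclassifies some women, whereas the outcome also accepts self-report. Adjusting for pre-index care also cannot remove changes in access to care after the index visit. Both points limit the benefit without removing it.

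**Conclusion.** The point holds as a gap in the stated covariate set. The plan provides for collecting prior care from the chart at baseline, does not name it for Aim I, and leaves its adjustment to a discretionary test that would miss a true 15-point imbalance about two times in three.

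Under the assumptions in step 2, the resulting bias is about 2 to 8 RD points if prior care is never adjusted for, about 1 to 2 points if it is tested and adjusted for only when significant, and near zero if it is always adjusted for and measured without error. These figures lie well inside the CI half-width of 18 to 20 points, so this gap does not by itself invalidate the pilot. The CI does not reflect systematic bias, however, and the estimate is to be carried into a later sample-size calculation. The documents do not show that the phases will actually differ in prior care. The case rests on the sequential design and the very low cost of protection.

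**What to change.** First, state when the outcome window starts, and whether an obstetric postpartum visit can count as the primary care outcome. If it can, item (a) below overlaps the outcome too.

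Then add to Table 1, as Aim I covariates for both groups, from the baseline chart review:
- (a) obstetric postpartum visit attended before the index WBV, yes/no;
- (b) own primary care visit at UIH in a fixed look-back period that does not overlap the outcome window, yes/no. This could be a set period before delivery, or any time before the index WBV if the outcome is restricted to visits after it.

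Enter both in the planned logistic model for the visit outcome whatever the balance test shows, and report the adjusted marginal RR and RD beside the crude ones. Present (a) by phase descriptively with a CI, and do not offer it as evidence for or against drift.

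The cost is two yes/no items from a review already planned, a little more abstraction and analysis, and a few sentences of text. State as a limitation that the covariates cover UIC care only, so adjustment is partial.
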